#### 17.3.4 HANDLING OF MISSING DATA

In the noncompartmental analysis, concentration data identified with NOS, NOR, and NOA will not be considered. Values that are below the limit of quantification (BLQ) and with no peak detectable (NOP) in the lag phase will be set to zero. The lag phase is defined as the period between time zero and the first timepoint with a concentration above the quantification limit. All other BLQ and/or NOP values of the profile will be ignored. Every effort will be made to include all concentration data in an analysis. If not possible, a case by case decision is required whether the value should be excluded.

[figure not shown]
Descriptive statistics of concentrations will be calculated only when at least 2/3 of the individuals have concentrations within the validated concentration range. The overall sample size to decide whether the '2/3' rule is fulfilled will be based on the total number of samples intended to be drawn for that time point (i.e., BLQ, NOR, NOS, NOA, NOP are included). Descriptive statistics of parameters are calculated only when at least 2/3 of the individual parameter estimates of a certain parameter are available.

**17.4 LIST OF** [REDACTED]

The table included in Section 10.4.1 presents a list of [REDACTED]

[REDACTED]

[REDACTED]

**17.5 COCKCROFT-GAULT FORMULA**

Glomerular filtration rate (GFR) may be estimated based on the commonly used and accepted formula, the Cockcroft-Gault formula:

$$GFR = \frac{(140 - \text{age}) \times \text{weight} \times F_s}{\text{Serum Creatinine} \times 72}$$

Units: GFR [ml/min], age [years], weight [kg], serum creatinine [mg/dl], FS is a correction Factor for Sex: in males FS = 1, in females FS = 0.85

**18 REVISION HISTORY**

**18.1 SUMMARY OF CHANGES**

**Protocol Version 3.0 dated 15MAY2018**  
**Replaces: Protocol Version 2.0 dated 22JAN2018 [Hungary]**  
**Replaces: Protocol Version 2.0 dated 19MAR2018 [Poland]**

The following table describes changes from Version 2.0 (dated 22JAN2018 [Hungary]) and Version 2.0 (dated 19MAR2018 [Poland]) with justifications provided. In Version 3.0, the two former country-specific protocols were combined into a single protocol for global standardization and compliance.

Section	Description	Country	Justification
Title Page	Change in Authorized Representative	
 
• Hungary
 
• Poland
 
	Due to staffing assignment changes within Alkahest, the Authorized Representative has been changed from [REDACTED]
Throughout	The exploratory endpoint of central retinal thickness (CRT) was changed to central subfield thickness (CST)	
 
• Hungary
 
• Poland
 
	
 
• Measurement of central retinal thickness (CRT) includes multiple subfields and must be performed by a central reader, which was not utilized in this study.
 
• Determination of central subfield thickness (CST) is a specific measurement of retinal thickness that is limited to a circular area of diameter of 1 mm from the center point of the retina that can be measured by investigators without the need for a central reader.
 

Throughout	Minor changes to grammar and formatting	
 
• Hungary
 
• Poland
 
	Grammar and formatting standardization.
List of Abbreviations	
 
• Added “CST: Central Subfield Thickness”
 
• Removed “OPU: Operative Unit”
 
	
 
• Hungary
 
• Poland
 
	
 
• Abbreviation added to accommodate clarified exploratory endpoint measurement.
 
• Abbreviation removed – not required in Protocol.
 

1.1	Change in Authorized Representative (Signatory) / Responsible Party	
 
• Hungary
 
• Poland
 
	Due to staffing assignment changes within Alkahest, the Authorized Representative (Signatory) / Responsible Party has been changed from [REDACTED]. The email address has also been updated to reflect this change.
5.1 and Throughout	Inclusion Criteria in bullet 1/sub-bullet 1: was updated to read as follows: “Persistent exudation of SRF and IRF as	Hungary	
 
• The term “monthly” lacks specificity and should be regarded as a period of 4 to 6 weeks between each IVT injection for the purposes of this protocol.
 
• In addition to Section 5.1, the statement “monthly IVT anti-VEGF therapy” is also used throughout the protocol. Per the revision, this statement should now be
 

	documented by SD-OCT and absence of improvement in visual acuity following 3 consecutive (approximately 4 to 6 weeks apart) IVT anti-VEGF injections, subject must have received their last injection 30 to 90 days prior to the initial screening visit”		
interpreted as “consecutive (approximately 4 to 6 weeks apart) IVT anti-VEGF injections.”
 
 
Information was previously communicated to Principal Investigators and Study Coordinators in a Clarification Memorandum dated April 9, 2018.
 

5.1 and Throughout	Inclusion Criteria in bullet 1/sub-bullet 1: was updated to read as follows: “Persistent exudation of SRF and IRF as documented by SD-OCT and absence of improvement in visual acuity following 3 consecutive (approximately 4 to 6 weeks apart) IVT anti-VEGF injections, subject must have received their last injection 30 to 90 days prior to the initial screening visit”	Poland	
 
The term “monthly” lacks specificity and should be regarded as a period of 4 to 6 weeks between each IVT injection for the purposes of this protocol.
 
In addition to Section 5.1, the statement “monthly IVT anti-VEGF therapy” is also used throughout the protocol. Per the revision, this statement should now be interpreted as “consecutive (approximately 4 to 6 weeks apart) IVT anti-VEGF injections.”
 
To shorten the time period from receipt of last IVT anti-VEGF injection relative to screening, the study will only include subjects who received their last IVT anti-VEGF injection within 30 to 90 days prior to the initial screening visit. 
 
Previously incorporated into ALK4290-202 V2.0 in Hungary.
 
 
 

5.1	Inclusion Criteria in bullet 1/sub-bullet 2: Changed “Central subfield retinal thickness to CST”	
 
Hungary
 
Poland
 
	Standardized nomenclature to align with clarified abbreviation.
5.1	
 
Inclusion Criteria in bullet 5 revised to designate country-specific requirements related to
 
	
 
Hungary
 
Poland
 
	
Bullet 5 now includes the following country-specific requirements:
 
 
Hungary: Female subjects must not be pregnant or breastfeeding. Women of childbearing potential and men must agree to use adequate contraception (hormonal or barrier method of birth control; abstinence) prior to study
 

	
pregnancy and pregnancy testing
 
 
The requirements have not changed in either country from V2.0 to V3.0 other than being combined to create a single protocol
 
		
entry. Should a woman become pregnant or suspect she is pregnant while she or her partner is participating in the study, she should inform her treating physician immediately
 
 
Poland: Female subjects must not be pregnant or breastfeeding. Women of childbearing potential must have a negative serum pregnancy test at screening/visit 1, the first treatment visit, and the last treatment visit. Women of childbearing potential and men must agree to use highly effective contraception (Clinical Trial Facilitation Group 2014) prior to study entry. A woman is considered of childbearing potential following menarche and until becoming postmenopausal (no menses for at least 2 years without an alternative cause). Should a woman become pregnant or suspect she is pregnant while she or her partner is participating in the study, she should inform her treating physician immediately
 

7.2.5.1	
Removed the following sentence: “As a further endpoint, the total retinal thickness, inclusive of the sub-RPE layer, will be measured.”
	
 
Hungary
 
Poland
 
	
Measurement of total retinal thickness includes multiple subfields and must be performed by a central reader, which was not utilized in this study.

8.2.1.1	
Serum pregnancy test required in Poland only added to bullet 5
	
Hungary
	
Per request from the Polish Department of Clinical Trials for Medicinal Products, added the following: “Poland only: serum pregnancy test (in women of childbearing potential).”

8.2.1.1	
Serum pregnancy test required in Poland only
	
Poland
	
Added “Poland only:” to indicate that serum pregnancy testing is not required in Hungary.

8.2.2.1	
Serum pregnancy test required in Poland only added to bullet 4
	
Hungary
	
Per request from the Polish Department of Clinical Trials for Medicinal Products, added the following: “Poland only: serum pregnancy test (in women of childbearing potential).”

8.2.2.1	
Serum pregnancy test required in Poland only
	
Poland
	
Added “Poland only:” to indicate that serum pregnancy testing is not required in Hungary.

8.2.3.1	
Serum pregnancy test required in Poland only added to bullet 3
	
Hungary
	
Per request from the Polish Department of Clinical Trials for Medicinal Products, added the following: “Poland only: serum pregnancy test (in women of childbearing potential).”

8.2.3.1	
Serum pregnancy test required in Poland only
	
Poland
	
Added “Poland only:” to indicate that serum pregnancy testing is not required in Hungary.

10.2	
 
• H0 updated to “Change from baseline in BCVA letter score = 0” was previously “Change from baseline in BCVA letter score > 0”
 
• H1 updated to “Change from baseline in BCVA letter score ≠ 0 with α1= 0.20” was previously “Change from baseline in BCVA letter score < 0 with α1= 0.025”
 
	
 
• Hungary
 
• Poland
 
	Statistical analyses updated to two-sided alpha between 0.05 and 0.20 versus one-sided approach used in previous version.
15.1	Removed superscript “5” from “Pharmacokinetics blood sample (for plasma extraction)” at Visit 9	
 
• Hungary
 
• Poland
 
	No treatment is administered at Visit 9. Thus, the sample can be performed at any time during visit – preferably at the end of all visit procedures.
15.1	Pregnancy test screening/visit 1, first treatment visit, and final treatment visit for subjects in Poland	Hungary	Per request from the Polish Department of Clinical Trials for Medicinal Products, added pregnancy test (as applicable per Inclusion Criteria in Poland) at screening/visit 1, first treatment visit, and final treatment visit.
15.1	Added superscript “9” and footnote to Pregnancy test indicating it is required in Poland only	
 
• Hungary
 
• Poland
 
	Superscript/footnote required to indicate this test is required in Poland only .
16.1	Added reference to define “highly effective” contraception	Hungary	Clinical Trial Facilitation Group. Recommendations related to contraception and pregnancy testing in clinical trials. Version 2014-09-15:1-13.

SD-OCT	Spectral Domain Optical Coherence Tomography
SOC	System Organ Class
SOP	Standard Operating Procedures
SRF	Subretinal Fluid
TEAE	Treatment-Emergent Adverse Event
VEGF	Vascular Endothelial Growth Factor
wAMD	Wet Age-Related Macular Degeneration
WBC	White Blood Cell Count
WHO	World Health Organization

1. Introduction

The purpose of this statistical analysis plan (SAP) is to describe the planned analyses and reporting for protocol ALK4290-202, Version 3.0 dated 15MAY2018 and Clarification Memorandum #2 dated 12JUL2018.

This SAP is being written with due consideration of the recommendations outlined in the most recent International Conference on Harmonization (ICH) E9 Guideline entitled Guidance for Industry: Statistical Principles for Clinical Trials and the most recent ICH E3 Guideline, entitled Guidance for Industry: Structure and Content of Clinical Study Reports (CSR).

This SAP describes the data that will be analyzed and the subject characteristics, efficacy, and safety assessments that will be evaluated. This SAP provides details of the specific statistical methods that will be used. The statistical analysis methods presented in this document will supersede the statistical analysis methods described in the clinical protocol. If additional analyses are required to supplement the planned analyses described in this SAP they may be completed and will be identified in the CSR.

2. Study Objectives

The primary objective of this study is to investigate the potential therapeutic effects of a 6-week, twice daily oral dosing regimen of ALK4290 on best corrected visual acuity (BCVA) in patients with refractory Wet Age-Related Macular Degeneration (wAMD) (i.e., following 3 consecutive [approximately 4 to 6 weeks apart] intravitreal [IVT] anti-vascular endothelial growth factor [VEGF] injections in the study eye). The secondary objectives are to assess the safety of the proposed dosing regimen.

3. Study Variables

3.1 Primary Variable

- Mean change from baseline in BCVA letter score as measured by the Early Treatment Diabetic Retinopathy Study (ETDRS) testing method at 6-weeks

3.2 Secondary Variable

- Safety as assessed by incidence, seriousness, and severity of adverse events (AE)

3.3 Exploratory Variables

- Changes in concentrations of ALK4290 in plasma at various time points
- Changes in central subfield thickness (CST), intraretinal fluid (IRF), subretinal fluid (SRF), and pigment epithelial detachment (PED) as measured by spectral domain optical coherence tomography (SD-OCT) and fundus photography/fundus angiography (FP/FA)
- Evaluation of pharmacogenomic characteristics and biomarkers in blood and plasma samples

3.4 Statistical Hypotheses

The null and alternative hypotheses for change from baseline in BCVA letter score as measured by ETDRS testing method are as follows:

H₀: Mean change from baseline in BCVA letter score at 6 weeks = 0

H₁: Mean change from baseline in BCVA letter score at 6 weeks ≠ 0

The hypothesis testing will be at a two-sided Type I error rate (α) of 0.20. Specifics of the statistical tests are provided in Section 14.

4. Study Design and Procedures

4.1 General Study Design

This is a single arm, open-label study to evaluate the therapeutic effects and safety of a 6-week treatment regimen of ALK4290 in patients with refractory wAMD. This study enrolls patients with refractory active Choroidal Neovascularization (CNV) secondary to AMD who have received at least three consecutive (approximately 4-6 weeks) IVT anti-VEGF injections prior to screening. All subjects will receive the investigational treatment ALK4290 at a daily dosage of 800 mg administered orally twice a day as 400 mg tablets for 6 weeks. At every visit, safety and tolerability assessments will occur. At specified visits, BCVA will be measured by the ETDRS testing method and morphological evaluations will be conducted utilizing SD-OCT and FP/FA.

The study eye is defined as the eye that meets all the inclusion criteria and none of the exclusion criteria. If both eyes meet the inclusion and none of the exclusion criteria, the study is selected by the investigator, per their discretion.

The overall duration of the study is approximately 10 months from study initiation (i.e., first subject enrolled) to study completion (i.e., last subject last visit) with a targeted recruitment of 30 subjects over the accrual period. The subject participation period is 10 weeks (6-week treatment plus 4-week follow-up), unless prematurely discontinued.

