## 5 STUDY ENROLLMENT AND WITHDRAWAL

### 5.1 INCLUSION CRITERIA

**In order to be eligible for inclusion, all subjects must meet the following criteria:**

- Men and women with refractory active CNV secondary to AMD, diagnosed by a retinal specialist with all the following characteristics and ophthalmic inclusion criteria applied to the study eye:
  - Persistent exudation of SRF and IRF as documented by SD-OCT and absence of improvement in visual acuity following 3 consecutive (approximately 4 to 6 weeks apart) IVT anti-VEGF injections; subject must have received their last IVT anti-VEGF injection 30 to 90 days prior to the initial screening visit
  - CST  $\geq$  250 microns on SD-OCT (exclusive of subretinal pigment epithelial fluid, inclusive of SRF)
  - Total lesion size not greater than 12 disc areas on FA
  - If present, subretinal hemorrhage must comprise  $<$  50% of the total lesion area on FA
  - No subfoveal fibrosis or atrophy on FA
- BCVA letter score, as measured by ETDRS in the study eye, between 70 and 24 letters, inclusive, at screening
- Patients 50 years of age or older at screening visit 1
- Body mass index (BMI) between 18 and  $\leq$  40 at screening visit 1
- **Hungary:** Female subjects must not be pregnant or breastfeeding. Women of childbearing potential and men must agree to use adequate contraception (hormonal or barrier method of birth control; abstinence) prior to study entry. Should a woman become pregnant or suspect she is pregnant while she or her partner is participating in the study, she should inform her treating physician immediately.
- **Poland:** Female subjects must not be pregnant or breastfeeding. Women of childbearing potential must have a negative serum pregnancy test at screening/visit 1, the first treatment visit, and the last treatment visit. Women of childbearing potential and men must agree to use highly effective contraception ([Clinical Trial Facilitation Group 2014](#)) prior to study entry. A woman is considered of childbearing potential following menarche and until becoming postmenopausal (no menses for at least 2 years without an alternative cause). Should a woman become pregnant or suspect she is pregnant while she or her partner is participating in the study, she should inform her treating physician immediately.
- Signed informed consent consistent with ICH-GCP guidelines and local legislation prior to participation in the trial, which includes medication washout and restrictions

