## 10 STATISTICAL CONSIDERATIONS

### 10.1 STATISTICAL DESIGN MODEL AND ANALYTICAL PLANS

The therapeutic effect of the treatment will be investigated in one single group of subjects, with no control group. The observed mean effect will be compared with 0 as reference value. Overall baseline and demographic data will be summarized using descriptive statistics.

Subject disposition (e.g., the number of subjects enrolled, completed, and discontinued) will be summarized and medical history data will be listed. Prior and concomitant medications taken from screening and during the study will be categorized by World Health Organization (WHO) classification for therapeutic class and drug name, listed and summarized by number and percentage of subjects.

Final analyses are not limited to the summaries described herein. Analytical details and assumptions will be fully presented in the SAP.

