Data management procedures, including database design and selection of the data dictionary will be performed by the Data Manager and reviewed and approved by the Sponsor. Auto-coding of all AEs, medical histories and concomitant medications will be performed by the IBM Clinical Development EDC system with additional manual coding performed by the Sponsor designated medical coder. Medical coding will be reviewed by the GCT Medical Monitor and confirmed and approved by the Sponsor. All reported study data will be recorded on the electronic Case Report Forms (eCRF) using IBM Clinical Development and transferred to SDC by ProTrials. Clinical personnel at the study site and the CRO are responsible for ensuring that the protocol is followed and that the eCRFs are properly completed.

Additional safety lab data external to the eCRF data will be provided by Synevo to ProTrials to be reconciled with the EDC data and transferred separately to SDC for analysis. External PK data will be transferred from KCAS and will be analyzed by SDC as outlined in the PK plan (separate from the SAP).

[REDACTED]

[REDACTED]

All Subject IDs will be assigned automatically within the EDC. The Subject ID consists of 9 numbers: the first set of 3 numbers are specific for the protocol number (i.e., 202); the second set of 3 numbers are specific for the site number (i.e., 001 through 012), and the third set of 3 numbers are the subject specific screening number (e.g., 001, 002, etc.).

After data are entered into EDC, data are reviewed and verified by the clinical monitoring/operations CRO and ProTrials Data Management. Additionally, SAE reconciliation of the Clinical Database is performed against the Alkapest Global Safety Database and any issues are resolved. When the database has been confirmed to be complete, consistent and accurate, the database will be locked according to ProTrials Standard Operating Procedures and study specific Data Management Plan. Any

Unless specified otherwise, all ocular assessments and efficacy outcome measures are with respect to the study eye, here hence. Data collected for the fellow eye (non-study eye) will be included in subject listings and may be analyzed.

Study day will be calculated as (Date of Visit) – (Date of Initiation of Investigational Medicinal Product [IMP]) + 1 for visits after initiation of IMP and as (Date of Visit) – (Date of Treatment Initiation) for visits prior to initiation of IMP.

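### When both eyes qualify, the study eye is left to the investigator's discretion, so an avoidable and probably small bias of unknown direction can enter the uncontrolled primary estimate

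*SAP*

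**What the plan says.** SAP section 4.1 defines the study eye by eligibility: "The study eye is defined as the eye that meets all the inclusion criteria and none of the exclusion criteria". For a subject with two such eyes it continues: "If both eyes meet the inclusion and none of the exclusion criteria, the study is selected by the investigator, per their discretion". A word is missing, but the meaning is clear.

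Protocol section 5.1 has its "ophthalmic inclusion criteria applied to the study eye" and does not say how that eye is chosen. Neither document, as supplied, gives a tie-break, asks for a reason, or says when the choice becomes final. The schedule of events (protocol 15.1, SAP 4.2) places eligibility checks and BCVA measurement at both Visit 1 and Visit 2. Visit 2 is the usual baseline (protocol section 7, SAP 9.2).

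The choice determines what is analysed. The SAP's general statistical text states that, unless specified otherwise, "all ocular assessments and efficacy outcome measures are with respect to the study eye". Protocol section 10.1 says: "The therapeutic effect of the treatment will be investigated in one single group of subjects, with no control group", and "The observed mean effect will be compared with 0 as reference value". SAP section 14 does this with a one-sample t-test, and SAP 3.4 sets the level: "The hypothesis testing will be at a two-sided Type I error rate (α) of 0.20". Fellow-eye BCVA appears only in listings (SAP 14).

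**The concern.** ALK4290 is taken orally, and protocol 6.4 allows no other intervention for wAMD. Naming one eye as the study eye therefore mainly decides which eye is measured for efficacy. Discretion serves no visible purpose there.

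The investigator may know each eye's injection history, lesion and recent acuity trend. A choice that draws on this, even unknowingly, selects on prognosis. In a randomised trial an eye chosen before allocation affects both arms alike and largely cancels. Here there is no second arm, so any selection effect goes directly into the mean compared with 0.

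Timing is a second route. Nothing prevents the choice from being settled after BCVA has been read at Visit 2. Picking an eye that happened to score low that day would build regression to the mean into the change score.

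No planned analysis would reveal either effect. SAP 11.1 tabulates right or left study eye but does not count subjects with two eligible eyes.

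**Working it through.** **Inputs from the documents.** 30 enrolled and about 25 evaluable (protocol 10.5, SAP 6); one-sample t-test at two-sided 0.20 (SAP 3.4, 14); an average loss of 10 ETDRS letters in a year without treatment (protocol 2.2); 6 weeks of treatment, or 42 days.

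**Assumed, not in the documents.** Fraction f of subjects with two eligible eyes: 10% to 20%, with 40% as a stress case. Advantage d of the chosen eye over its fellow: 3 to 5 letters. SD of BCVA change: 5 to 10 letters. Correlation r between the investigator's prediction and the actual change: 0.3 to 0.5. Between-eye correlation of change: 0 to 0.3.

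**Step 1: the plan's own figure.** There is none to reproduce. The documents give no SD, effect size or power, and no rate of bilateral eligibility.

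**Step 2: shift against a neutral rule.** A neutral rule takes the better eye about half the time, so its expectation is the average of the two eyes. An eye that does d letters better than its fellow lies d/2 above that average.

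Shift = f × d/2

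- Low: 0.10 × 3/2 = 0.15 letters
- High: 0.20 × 5/2 = 0.50 letters

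**Step 3: second route to the same size.** If the eye with the better predicted change is always taken and the eyes are independent, the shift is f × r × 0.564 × SD, where 0.564 is the expected larger value of two standard normals.

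- Low: 0.10 × 0.3 × 0.564 × 5 = 0.08 letters
- High: 0.20 × 0.5 × 0.564 × 10 = 0.56 letters

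The implied between-eye advantage at SD 8 is 2 × r × 0.564 × 8, which is 2.7 letters at r = 0.3 and 4.5 at r = 0.5. This is close to the 3 to 5 letters assumed in step 2.

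**Step 4: scale.** With n = 25, p < 0.20 needs a mean change of t(0.90; 24 df) × SD/√25 = 1.318 × SD/5. That is 1.3, 2.1 or 2.6 letters at SD 5, 8 or 10. A shift of 0.15 to 0.5 is 7% to 24% of the SD 8 threshold. The protocol's untreated loss, scaled linearly, is 10 × 42/365 = 1.15 letters in 6 weeks. The shift is 0.13 to 0.43 of that.

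**Step 5: error rates.** Simulation of a true null, n = 25, 40,000 replicates per scenario, with the investigator always favouring the eye with the better predicted change. Ranges cover r of 0.3 to 0.5 and between-eye correlation of 0 to 0.3.

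| f | Mean shift at SD 8 (letters) | Two-sided rejection | Favourable tail |
|---|---|---|---|
| 0 (neutral) | about 0 | 0.20 | 0.10 |
| 10% | 0.09–0.21 | 0.199–0.205 | 0.111–0.125 |
| 20% | 0.19–0.44 | 0.204–0.219 | 0.121–0.158 |
| 40% | 0.38–0.90 | 0.216–0.264 | 0.150–0.233 |

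The two-sided error barely moves at 10% to 20%. The favourable tail rises more, because selection in one direction moves rejections from one side to the other. If investigators favoured the eye with the poorer outlook, the result would be mirrored.

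**The case against.** The affected group may be very small. Both eyes would have to meet every study-eye criterion in protocol 5.1, including persistent fluid without acuity gain after three consecutive injections, a last injection 30 to 90 days before screening, and the CST and BCVA limits. Protocol 5.2 then excludes anyone with planned anti-VEGF treatment in the fellow eye. Ten to twenty per cent of 30 is only 3 to 6 people, and even that rate is assumed. The SAP describes the study as early phase and exploratory (9.5), and it is not powered (SAP 6). These points stand and keep the concern small. They do not remove it: the SAP still runs a formal test, and the protocol says a favourable result could support longer studies.

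Four stronger readings are tempting, and the documents do not support them.

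- A reader might infer that investigators did pick favourable eyes. The text shows only that they could. An investigator might equally take the worse eye.
- A reader might multiply the bilateral fraction by the full between-eye difference and get 0.3 to 1.0 letters, close to the 1.15-letter untreated loss. That would be right only if a neutral rule always took the eye that did worse.
- A reader might blame the open label. The choice presumably precedes dosing, before any response is visible. The missing control group matters more.
- A reader might say that a comparison of study eye with fellow eye is spoiled. None is planned for BCVA. Most fellow eyes would probably fail the entry criteria, so the eyes would differ under any rule.

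**Conclusion.** The concern holds as a modest, avoidable weakness. A stated discretion rule governs which eye supplies the primary endpoint, its timing is open, and no control group offsets it. On the stated assumptions the primary mean could shift by about 0.15 to 0.5 letters, in an unknown direction. The two-sided error would stay near 0.20 to 0.22, and the chance of a false favourable result would rise from 0.10 to at most about 0.16 with up to 20% bilateral eligibility. A material effect would need many more bilateral cases, as in the 40% row.

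Every size here rests on assumed values for bilateral eligibility, prediction and SD. The SAP also refers to a clarification memorandum (section 1) that was not available. If it contains a selection rule, SAP 4.1 should state that rule.

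**What to change.** Replace the discretion clause in SAP 4.1 and put the same sentence in protocol 5.1, because sites choose the eye under the protocol. The rule should not depend on outcome or prognosis. For example, if both eyes qualify at Visit 1, the study eye is the right eye when the subject's screening number is odd and the left eye when it is even; the choice is recorded before BCVA is measured at Visit 2. The screening number is already part of the automatically assigned subject ID (SAP section 7).

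A rule that takes the eye with the lower Visit 1 BCVA would be objective but not neutral. It favours eyes with more room to gain. Some regression to the mean could also remain, since Visit 2 normally follows within days and baseline reverts to Visit 1 if the Visit 2 value is missing.

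Report the number of subjects recorded as having two eligible eyes, from data already collected. OCT and angiography are specified for the study eye (protocol 7.2.5.1, 7.2.5.2), so this count may be incomplete; added fellow-eye imaging is not proposed. If enrolment has already advanced, add a sensitivity analysis of the primary endpoint that excludes those subjects.

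The cost is one sentence in each document, one reported count and, if needed, one extra run of the primary analysis. The downside is that investigators lose a free choice in the few bilateral cases.
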